7.3.1 Primary endpoint analyses

The primary endpoint of the study is PFS rate at 6 months (PFS6). This will be calculated as the proportion of patients who are alive and without disease progression at the 24-week tumour assessment, out of all analysed patients. Patient prematurely discontinued without the 24-week assessment will be considered as not achieving PFS6 regardless of the reason for discontinuation.

For Cohort A, the first stage will include 25 patients treated with Afatinib, as described in [Section 7.4](#). When the criteria for transition into the second stage are met, the study will move on to the full accrual and there will be up to 70 patients treated in Cohort A.

At the end of the second stage, the significance level for testing the null hypothesis H_0 : PFS6 \leq 40% will be calculated as the exact binomial probability i.e. $\text{Prob}(X \geq s | n, p=0.40)$, where 's' is the observed number of patients achieving PFS6 and 'n' is the total number of patients. A Wilson 90% confidence interval will be provided also.

PFS6 for Cohort B patients will be analysed descriptively when all patients in Cohort B have completed the 24-week tumour assessment.

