7.3.2 Secondary endpoint analyses

Key Secondary Endpoint

Objective response rate (ORR) defined as the proportion of patients with confirmed complete response (CR) or confirmed partial response (PR) is the key-secondary endpoint.

At the end of the second stage, the significance level for testing the null hypothesis $H_0: ORR \leq 5\%$ will be calculated as the exact binomial probability i.e. $\text{Prob}(X \geq s | n, p=0.05)$, where 's' is the observed number of patients achieving a confirmed objective response and 'n' is the total number of patients. A Wilson 90% confidence interval will be provided also.

Other Secondary Endpoints

Progression-free survival will be analysed by Kaplan-Meier method. Clinical deterioration without image-based progression will not be counted towards progression. Detailed censoring rule for PFS and sensitivity analysis will be specified in the Trial Statistical Analysis Plan (TSAP).

Disease control rate (DCR) defined as the proportion of patients with confirmed CR, PR or stable disease (SD) will be analysed similarly to ORR.

Duration of objective response is defined as the time from first documented CR or PR to the time of progression or death. Duration of objective response will be summarized descriptively.

Kaplan-Meier estimates of overall survival will be provided.

Tumor shrinkage from baseline will be summarized descriptively and by waterfall plot of the maximum percentage decrease from baseline of the sum of the longest diameters of target lesions will be presented.

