7.4 INTERIM ANALYSES

PFS6 and confirmed ORR will be evaluated for the first 25 treated patients when the last patient among them completes the 24-week tumor assessment. If 12 or more patients achieve PFS6, or at least 2 have a confirmed response, the study will move on to the full targeted accrual in Stage 2. The primary analysis will be conducted when 70 patients in Cohort A complete the 24-week tumor assessment.

If fewer than 12 patients achieve PFS6 and fewer than 2 patients have a confirmed response, the trial will be stopped for futility. All patients enrolled will be followed until disease progression and a full analysis will be carried out after all patients discontinue the study.

Stages 1 and 2 of the study will be conducted in a seamless fashion with no interruption in enrolment after treating 25 patients. Therefore by the time of the futility assessment, more than 25 patients might have been treated. The sponsor may however suspend recruitment after enrolling the pre-defined 25 patients in Stage 1 in the event of low likelihood to meet the criteria to move from Stage 1 to Stage 2.

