7.7 DETERMINATION OF SAMPLE SIZE

[Table 7.7: 1](#) shows that 70 patients would be expected to provide approximately 90% power for PFS6, with PFS6=60% under the alternative hypothesis and PFS6=40% under the null. Although the Stage 1 futility criterion will reduce the power, the power after adjustment for the futility analysis would likely be between the unadjusted and adjusted power estimates in [Table 7.7:1](#), because the futility criterion allows the trial to proceed to Stage 2 with fewer than 12 patients with successful PFS6, provided at least two patients have confirmed response.

Table 7.7: 1 Power¹ for PFS6 in Cohort A, with PFS6=60% under the alternative hypothesis.

	N=65	N=70	N=75
Without adjustment for Stage 1			
alpha=0.025	87.2%	90.9%	93.6%
alpha=0.050	91.7%	94.3%	96.0%
With adjustment for Stage 1 (N=25, PFS6≥12)			
alpha=0.025	83.5%	86.3%	88.2%
alpha=0.050	87.1%	88.8%	89.9%

¹Based upon simulating one million samples under the alternative hypothesis of PFS6=60%. For each sample a significance level was calculated as the binomial probability ($X \geq s | n, p=0.40$), where 's' is the observed number of patients achieving PFS6 and 'n' is the total number of patients.

Table 7.7: 2 shows that 70 patients would be expected to provide approximately 80% power for ORR, with ORR=15% under the alternative hypothesis and ORR=5% under the null.

Tables 7.7:1 and 7.7:2 present power for both alpha=0.025 and 0.05 because the Hochberg multiplicity procedure would compare the higher of the observed significance levels for PFS6 and ORR to 0.05. If the larger significance level is smaller than 0.05, then we can reject null hypothesis for both PFS6 and ORR. If the larger significance level is greater than 0.05, then the smaller significance level would be compared to a more stringent threshold 0.025, in order to refrain the family-wise error rate at 0.05.

If the underlying PFS6 rate is 40%, the probability of observing fewer than 12 patients out of 25 in Stage 1 would be 73%. Under the alternative that PFS6=60%, the chance of observing at least 12 patients would be 92%.

For ORR under the null ORR=5%, the probability of observing fewer than 2 confirmed responses in Stage 1 would be 64%. Under the alternative that ORR=15%, the chance of observing at least 2 responses would be 91%.

For Cohort B the analyses will be exploratory and descriptive in nature and the sample size is determined based on feasibility and practical considerations.

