## 7.4 PRIMARY ENDPOINT

The primary endpoint of this study is progression free survival rate at 6 months (PFS6), determined as being alive and progression-free at the 24-week assessment.

Patients who are alive and progression-free at the 24-week (168-day) assessment will be considered successes for PFS6. The following rules are required for PFS6 to be considered a success:

- 1) Consider only valid assessments done before starting of any new anticancer therapy. Also do not consider any assessments done after EOT date+ 30 days.
- 2) Patient has at least one valid assessment demonstrating non-progression on or after day 168 with reference to treatment start day.
- 3) Patient who did not meet the second criterion but has at least one valid non-PD assessment on or after day 154 (22 weeks) and has progression documented after day 182 (26 weeks) is considered as success for PFS6.

Examples:

- i) With SD at Day 156 followed by PD at Day 183 will be considered as success for PFS6.
- ii) With SD at Day 146 followed by PD at Day 170 will not be considered as success for PFS6.
- iii) With SD at Day 156 followed by PD at Day 170 will not be considered as success for PFS6.

For Cohort A, at the end of stage 2, final goal is to test  $H_0: PFS6 \leq 40\%$  vs alternative:  $H_a: PFS6 > 40\%$ . **If we observe fewer than 12 PFS6 successes and fewer than 2 objective responses among the first 25 patients in Stage 1, enrollment for Cohort A will be terminated, and the null hypothesis will be accepted.**

At the end of Stage 2, the significance level for testing the null hypothesis will be calculated as the exact binomial probability i.e.  $\text{Prob}(X > s | n, p = 0.40)$ , where 's' is the observed number of patients achieving PFS6 and 'n' is the total number of patients. A Wilson 90% confidence interval will be provided also.

If trial stops at stage 1, for cohort A, PFS6 will be analysed descriptively and no formal statistical testing will be performed.

PFS6 for Cohort B patients will be analysed descriptively when all patients in Cohort B have completed the 24-week tumour assessment.

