## **7.5 SECONDARY ENDPOINTS**

### **7.5.1 Key secondary endpoint**

Each patient will be assigned to one of the following RECIST categories: CR, PR, SD, Non-CR/Non-PD (NN), PD or Not Evaluable (NE), irrespective of protocol violations or missing data.

Objective response is defined as CR or PR, with confirmation as specified by RECIST 1.1.

A summary of confirmed objective response rate (ORR) using the investigator assessment of best overall response will be produced.

The null hypothesis for this key secondary endpoint ORR is  $H_0: \text{ORR} \leq 5\%$  and the alternative  $H_a: \text{ORR} > 5\%$ .

At the end of the second stage, for cohort A, the significance level for testing the null hypothesis  $H_0: \text{ORR} \leq 5\%$  will be calculated as the exact binomial probability i.e.  $\text{Prob}(X > s | n, p = 0.05)$ , where 's' is the observed number of patients achieving a confirmed objective response and 'n' is the total number of patients. A Wilson 90% confidence interval will be provided also.

A Hochberg multiple adjustment procedure will be used to control the family-wise error rate at 0.05 (one-sided) for testing PFS6 and ORR.

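### The SAP leaves the observed count out of both exact p-values (X > s instead of the protocol's X ≥ s), which lowers each rejection limit by one patient and roughly doubles the family-wise error at n = 70

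*SAP*

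**What the plan says.** Both documents plan two one-sided exact binomial tests at the end of Stage 2 in Cohort A, of PFS6 against 40% and of ORR against 5%. They define the p-value differently.

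| Endpoint | Protocol | SAP |
|---|---|---|
| PFS6 | 7.3.1: "X \geq s | n, p=0.40)$, where 's' is the observed number of patients achieving PFS6" | 7.4: "X > s | n, p = 0.40)$ , where 's' is the observed number of patients achieving PFS6" |
| ORR | 7.3.2: "X \geq s | n, p=0.05)$, where 's' is the observed number of patients achieving a confirmed objective response" | 7.5.1: "X > s | n, p = 0.05)$ , where 's' is the observed number of patients achieving a confirmed objective response" |

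The footnotes to protocol Tables 7.7:1 and 7.7:2 repeat the ≥ form. SAP 7.5.1 keeps the protocol's multiplicity commitment: "A Hochberg multiple adjustment procedure will be used to control the family-wise error rate at 0.05 (one-sided) for testing PFS6 and ORR". Protocol 7.7 explains the second Hochberg step: if the larger p-value exceeds 0.05, "the smaller significance level would be compared to a more stringent threshold 0.025". SAP Section 3 says the SAP is based on protocol Section 7. SAP Section 4 declares one change, to the futility criterion, and none to the p-value.

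**The concern.** A one-sided exact p-value is the probability, under the null, of a result at least as extreme as the one observed. Prob(X > s) drops the probability of the observed count itself. Taken literally, it gives p = 0 for 70 successes out of 70.

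Small discrete samples make this matter, because a single count near the limit carries between one and four percentage points of null probability. The SAP is the document that will be programmed. If it is followed literally, the primary or key secondary test can be declared positive at counts whose true p-value is above the stated limit. The tests would also no longer be those behind the protocol's power tables.

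**Working it through.** **Inputs.** n = 70 (protocol 7.4: "The primary analysis will be conducted when 70 patients in Cohort A complete the 24-week tumor assessment"). PFS6 rates: "with PFS6=60% under the alternative hypothesis and PFS6=40% under the null" (protocol 7.7). ORR is 5% under the null and 15% under the alternative (protocol 7.7). Hochberg limits are 0.05 and 0.025, one-sided. Stage 1 continues if at least 12 of 25 patients reach PFS6 or at least 2 have a confirmed response (protocol 7.4). SAP 7.4 makes the stop binding. The documents do not give the association between PFS6 and response, so it is varied.

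**Step 1: which formula reproduces the protocol's power at N = 70, without the Stage 1 adjustment?**

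| | Protocol table | With X ≥ s | With X > s |
|---|---|---|---|
| PFS6, 0.025 | 90.9% | 90.9% | 94.3% |
| PFS6, 0.05 | 94.3% | 94.3% | 96.5% |
| ORR, either level | 84.2% | 84.3% | 91.6% |

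With the Stage 1 adjustment, the ≥ form gives 86.3% and 88.8% for PFS6 and 79.7% for ORR. The tables show 86.3%, 88.8% and 79.6%. The design was built on ≥.

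**Step 2: null tail probabilities at n = 70.**

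- PFS6, p = 0.40: P(X ≥ 35) = 0.0574; P(X ≥ 36) = 0.0347; P(X ≥ 37) = 0.0199.
- ORR, p = 0.05: P(X ≥ 7) = 0.0604; P(X ≥ 8) = 0.0234.

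Because Prob(X > s) = Prob(X ≥ s + 1), the SAP gives each count the p-value that belongs to the next count up.

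| Test | Protocol rejects from (true size) | SAP rejects from (true size) |
|---|---|---|
| PFS6 at 0.05 | 36/70 (3.5%) | 35/70 (5.7%) |
| PFS6 at 0.025 | 37/70 (2.0%) | 36/70 (3.5%) |
| ORR at 0.05 or 0.025 | 8/70 (2.3%) | 7/70 (6.0%) |

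At 7/70 responses the SAP's p is 0.023, which passes the 0.025 step alone; the correct p is 0.060, which fails 0.05. At 35/70 on PFS6 the SAP's p is 0.035 and the correct value is 0.057.

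**Step 3: Hochberg family-wise error with both nulls true.** The ORR limit is the same at both levels, so the procedure rejects something whenever ORR reaches its limit or PFS6 reaches its 0.025 limit. For independent endpoints without the Stage 1 stop:

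- Protocol form: 1 − (1 − 0.0234)(1 − 0.0199) = 0.043.
- SAP form: 1 − (1 − 0.0604)(1 − 0.0347) = 0.093.

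The exact joint distribution of the two counts gives the other cases:

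| | X ≥ s | X > s |
|---|---|---|
| No Stage 1 stop | 4.1–4.3% | 8.9–9.3% |
| Binding Stage 1 stop | 3.7–3.9% | 7.7–8.1% |

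The lower end of each range is every responder being a PFS6 success; the upper end is independence. In the implausible case that no responder is a PFS6 success, the SAP form gives 9.4% and 8.3%.

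**The case against.** **Typing slip or lost symbol.** The SAP sentences otherwise follow the protocol closely and Section 4 declares no such change, so a transcription slip is the likely cause. A symbol lost in text conversion cannot be fully excluded either: the ≤ signs in the same SAP sections survive, but no ≥ appears elsewhere in the SAP text for comparison. Against that, the protocol's ≥ signs came through, and both SAP formulas read the same way. A slip in the document that is programmed still needs correcting.

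**n = 70 is an unfavourable size.** This is true. With the binding stop and independent endpoints, the SAP form gives 5.2% at n = 60, 6.6% at 65, 8.1% at 70, 4.7% at 71, 5.3% at 72, 5.5% at 74 and 6.4% at 75. Enrolment is seamless, so the final n may differ from 70. But 70 is the planned size, the rate is above 5% at all of these sizes except 71, and it stays at about twice what the correct formula gives.

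**Few results are affected.** Only boundary counts change the conclusion: exactly 7 responses, PFS6 at 36, or PFS6 at 35 when ORR also passes. The planned Wilson 90% interval has a lower bound of 40.4% at 35/70 and 5.5% at 7/70, so it already excludes the null there. It is an approximate interval, however, and cannot validate a p-value described as exact. If the trial stops at Stage 1, no formal test is done.

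**The trial is exploratory.** Both documents say so, and the protocol synopsis calls the analyses descriptive. This limits the regulatory consequence. It does not remove the explicit commitment to control the family-wise error at 0.05.

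**Conclusion.** The concern holds. The two documents contradict each other on the primary and key secondary p-values, the SAP form is incorrect, and the protocol's power tables confirm that ≥ was intended. At n = 70 both rejection limits drop by one patient. The family-wise error is about 8–9%, against about 4% for the correct tests: roughly double what the correct formula attains, and about 1.5 to 1.9 times the nominal 5%.

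These figures assume exactly 70 evaluable patients, both null rates true at their boundary (40% and 5%), and literal programming of the SAP formula. They change with n, with the PFS6–response association and with whether the Stage 1 stop is applied. The defect in the formula depends on none of these. It must be fixed before the final analysis because it can reverse the conclusion on either tested endpoint.

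**What to change.** In SAP 7.4 and 7.5.1, replace Prob(X > s | n, p) with Prob(X ≥ s | n, p), and check that the analysis code adds the probability of the observed count to the upper tail.

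State the resulting limits as a programming check, labelled as applying to n = 70 only: PFS6 at least 36 (0.05) or at least 37 (0.025), and ORR at least 8 (both levels). If the final n differs, the limits must be recomputed; at n = 71, for instance, the ORR limit at 0.025 is 9.

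The cost is two symbols and the matching code. Nothing changes in conduct, data collection or sample size. The rejection limits rise by one patient, back to those on which the protocol's power was calculated, so no planned power is lost.

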## **7.5 SECONDARY ENDPOINTS**

### **7.5.1 Key secondary endpoint**

Each patient will be assigned to one of the following RECIST categories: CR, PR, SD, Non-CR/Non-PD (NN), PD or Not Evaluable (NE), irrespective of protocol violations or missing data.

Objective response is defined as CR or PR, with confirmation as specified by RECIST 1.1.

A summary of confirmed objective response rate (ORR) using the investigator assessment of best overall response will be produced.

The null hypothesis for this key secondary endpoint ORR is  $H_0: \text{ORR} \leq 5\%$  and the alternative  $H_a: \text{ORR} > 5\%$ .

At the end of the second stage, for cohort A, the significance level for testing the null hypothesis  $H_0: \text{ORR} \leq 5\%$  will be calculated as the exact binomial probability i.e.  $\text{Prob}(X > s | n, p = 0.05)$ , where 's' is the observed number of patients achieving a confirmed objective response and 'n' is the total number of patients. A Wilson 90% confidence interval will be provided also.

A Hochberg multiple adjustment procedure will be used to control the family-wise error rate at 0.05 (one-sided) for testing PFS6 and ORR.

### **7.5.2 Other Secondary endpoints**

PFS is determined as the time (months) from the date of first administration of Afatinib to the date of disease progression, or date of death (if a patients dies without progressing). The date of progression for the primary analyses will be determined based on assessments made by the investigators. All treated patients will be included.

[Table 7.5.2: 1](#) describes rules that can be used for sensitivity analyses to determine whether or not patients have had a PFS event (progression or death) along with the date of event or date of censoring (for those with no event).

These censoring rules will be used as a sensitivity analysis. Any additional sensitivity analyses that relax part of the rules will be determined later and will be mentioned in technical SAP.

Kaplan–Meier curve and associated tables will be produced for overall survival.

A summary of disease control rate using the investigator assessment of response will be produced. Disease control rate (DCR) is defined as the proportion of patients with best overall response as complete response (CR), partial response (PR) or stable disease (SD)

Following analysis for time to response, duration of response, tumor shrinkage will be done after completion of stage 2.

Time to objective response (TTR) is the time from first afatinib administration to the date of first documented CR or PR. This analysis will be based on treated set.

The duration of objective response (DOR) is the time from first documented CR or PR to the time of progression or death. This analysis will be based on responders set only.

Time to response will be summarised by the planned imaging time points. Descriptive statistics will be calculated for the duration of objective response and duration of disease control, where applicable patients will be censored as for the PFS primary analysis.

Waterfall plots (and associated tables) of the maximum percentage reduction from baseline sum of target lesion diameters will be presented for each cohort.

Table 7.5.2: 1 Rules to determine events and censoring for sensitivity analyses of PFS

Rule #	Situation	Outcome (event or censored)	Date of PFS event or censoring
1	No baseline tumour assessment (no death before second scheduled assessment)	censored	Date of the start of afatinib
2	Progressed from imaging (no missed radiologic assessments)	event	Date of PD
3a	Non-PD from imaging  , death before next scheduled assessment	event	Date of death
3b	Non-PD from imaging  , one missed assessment, death or progression after date of missed assessment, but before a second scheduled assessment	event	Date of PD or death
3c	Non-PD from imaging  , more than one consecutive missed assessment, death or progression after date of second missed assessment	censored	Date of last imaging before missed assessment
3d	Non-PD from imaging  , more than one consecutive missed assessment, non-PD according to imaging after missed assessments	censored	Date of last non-PD imaging
4	New anti-cancer medication before progression or death	censored	Date of last imaging before new anti-cancer medication
5	Death before the scheduled date of first imaging	event	Date of death
6a	No imaging performed post-baseline, patient dies between first and second scheduled assessments	event	Date of death
6b	No imaging performed post-baseline, patient dies after second scheduled assessment	censored	Date of the start of afatinib
6c	No imaging performed post-baseline, vital status is unknown or patient known to be alive	censored	Date of the start of afatinib
7	Alive and not progressed from imaging (no missed assessments)	censored	Date of last imaging

 From the last assessment at which CR, PR or SD was assessed.

## **7.7 EXTENT OF EXPOSURE**

Total treatment time (days and number of courses) will be calculated for each patient; off-drug periods due to non-compliance or toxicity prior to permanent discontinuation will be included as treatment time. In addition, the total treatment time will be summed over all patients and transformed to patient years. Standard descriptive summaries of these data will be provided for the treated set of patients.

Further summaries will also be produced:

- Treatment time (days) broken down by each dose level (40 mg, 30 mg and 20 mg for afatinib).
- Number and proportion of patients on each dose level over time.
- Time to first dose reduction and duration (days) of off-drug periods prior to first dose reduction.

## **7.8 SAFETY ANALYSIS**

All safety analyses will be performed on the treated set.

### **7.8.1 Adverse events**

Unless otherwise specified, the analyses of AEs will be descriptive in nature. All analyses of AEs will be based on the number of patients with AEs and NOT on the number of AEs. The reporting and analyses of AEs will follow the BI guideline (4). AEs will be coded with the most recent version of MedDRA®. The severity of AEs will be scaled according to the Common Terminology Criteria for Adverse Events (CTCAE) version 4.03.

Furthermore, for analysis of AE attributes such as duration, severity, etc. multiple AE occurrence data on the CRF, will be collapsed into AE episodes provided that all of the following applies:

- The same MedDRA lowest level term was reported for the occurrences

- The occurrences were time-overlapping or time-adjacent (time-adjacency of 2 occurrences is given if the second occurrence started on the same day or on the day after the end of the first occurrence)
- Treatment did not change between the onset of the occurrences OR treatment changed between the onset of the occurrences, but no deterioration was observed for the later occurrence

AE episodes will be condensed into AE records provided that the episodes were reported with the same term on the respective MedDRA level and that the episodes are assigned to the same treatment. For further details on summarization of AE data, please refer to the guideline 'Handling and summarization of adverse event data for clinical trial reports and integrated summaries'. (4)

For further details on summarization of AE data, please refer to (3, 4).

The analysis of AEs will include all events with onset in the on-treatment period (between treatment start date and (last date of trial medication + 30 days)) and residual effect period. Events occurring before first drug intake will be assigned to 'screening', and all events occurring after the residual effect period will be assigned to 'Post-study/follow-up'.

- An overall summary of AEs will be presented.

The frequency of patients with AEs will be summarised by highest CTC grade (grade 3, 4, 5 and all grades to allow both cohorts to fit on one page), treatment, primary system organ class and preferred term (PT). Separate tables will be provided for patients with each of the following AE categories:

- AEs by treatment, highest CTCAE, using SOC and PT
- Drug related AEs, as assessed by investigators, by treatment, highest CTCAE, using SOC and PT
- AEs leading to dose reduction by treatment, highest CTCAE, using SOC and PT
- AEs leading to afatinib discontinuation by treatment, highest CTCAE, using SOC and PT
- Serious AEs by treatment, highest CTCAE, using SOC and PT
- Drug related serious AEs by treatment, highest CTCAE, using SOC and PT
- AEs leading to death by treatment, highest CTCAE, using SOC and PT
- other significant AEs using SOC and PT ( see definition below)
- AEs of special interest (discussed below)

The system organ classes will be sorted according to the standard sort order specified by EMA, preferred terms will be sorted by frequency (within system organ class).

